The APRIL Trial initially planned to recruit up to 2500 patients via a remote recruitment model, however this protocol was not approved by the regulator (MHRA) so it was agreed that the trial would recruit through NHS GP surgeries until sufficient safety data was gathered (at least 100 patients) to support modifying the monitoring protocol to allow faster recruitment. However, it took longer than anticipated to recruit the first 105 patients by which time the Long COVID patient numbers, NHS support for Long COVID services and other factors had changed considerably. It was therefore decided by the Trial Steering Committee that the trial should be halted with the initial 105 patients recruited, and trial data analysed, to inform decisions around the design of a future trial and inclusion of the most appropriate individuals. The original set of analyses will still be conducted as laid out in the protocol although the primary outcome analysis is expected to be underpowered (based on the effect size assumptions in the original power calculation). The safety outcome analyses are anticipated to be particularly informative, given the absence of quality clinical data on the safety profile of Ashwagandha for this patient population. This may help to inform the general public regarding the safety of their usage of Ashwagandha (which is a popular over-the-counter supplement) as well as the design of future randomised trials of this product.

2 Study Objectives

Primary – to determine the effectiveness of Ashwagandha tablets (3-month course) for improving functional status at 3 months (measured by the Post-COVID-19 Functional Status Scale) among people experiencing ongoing symptoms of COVID-19.

Secondary – to determine the safety of Ashwagandha tablets (3-month course) and effectiveness for improving quality of life, reported fatigue, breathlessness, pain, sleep quality, mental health, cognitive function, work status and other symptoms at 3 months.

3 Study Design

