3.4 Study Assessments

3.4.1. Trial outcomes

Primary outcome measure

Self-reported functional status measured using the Post-COVID-19 Functional Status Scale (PCFS), at 3 months². Functional status is a key patient-centred indicator which measures the extent to which a condition limits a person's ability to conduct their usual activities. The PCFS has gained widespread popularity as a tool for measuring self-assessed functional status in Long COVID in trials and observational studies and has been translated into multiple languages. It was based on a similar, widely-used functional scale for stroke patients, and has been

validated in Long COVID patients³. The PCFS asks patients to consider a flow-chart of options that describe the extent of limitations to their daily activities over the past week. Based on the flow chart, they assign themselves to a grade between 0 (no functional limitations) to 4 (severe functional limitations).

Secondary outcome measures (all at 3 months)

- Quality of life by PROMIS 29+2 summary score,
- Self-reported fatigue, pain, sleep, anxiety, depression and social, physical and cognitive function by PROMIS 29+2 individual dimensions
- Self-reported breathlessness by modified MRC Dyspnoea Scale
- Health utility by EQ 5D-5L utility score
- Work status and productivity
- Other self-reported symptoms

Outcomes domains were selected to cover the most relevant key indicators for patients and policy makers as well as the most common symptoms of Long COVID. Outcome questionnaire instruments were chosen following thorough review of the literature and other ongoing studies, on the basis of wide use/validation, short length (to reduce participant burden), and relevance for this study population (ideally used successfully in Long COVID patients before). For outcome scores that required derivation, the approach used in the primary publication will be applied (PROMIS scores⁴ and EQ 5D-5L utility score⁵ using the most recent UK-based value set).

Safety outcomes

- SUSARs
- Severe adverse events (including pregnancies)
- All adverse events
- Adverse events related to liver function abnormalities
- Liver function test parameters

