6.2 Secondary outcomes

Due to the large number of secondary outcomes, the PROMIS-29+2 summary score and EQ-VAS score will be considered as 'key secondary outcomes' and only these (along with the primary outcome) will be taken forward into the additional analyses (section 8). For all secondary outcomes, the main analysis will be intention-to-treat complete case analysis at 3-month follow-up, and for continuous and ordinal outcomes these will be adjusted for baseline level of the same outcome. The statistical models that we plan to use for each outcome are listed below. Distributional checks will first be conducted to ensure that key assumptions for each planned model type are met, and if for any given outcome there are violations that threaten the validity of the proposed model type, that outcome will be binarized by the median value and analysed with binary logistic regression.

Ordinary least squares (linear) regression:

- Quality of life by PROMIS 29+2 summary score
- Self-reported fatigue by PROMIS 29+2 fatigue dimension
- Self-reported sleep disturbance by PROMIS 29+2 sleep dimension
- Self-reported anxiety by PROMIS 29+2 anxiety dimension
- Self-reported depression by PROMIS 29+2 depression dimension
- Self-reported social participation by PROMIS 29+2 social function dimension
- Self-reported physical function by PROMIS 29+2 physical function dimension
- Self-reported cognitive function by PROMIS 29+2 cognitive function dimension
- Self-reported pain interference by PROMIS 29+2 pain dimension
- Self-reported pain intensity by PROMIS 29+2 0-10 pain rating scale
- Health utility by EQ 5D-5L utility score
- EQ VAS score
- Self-reported work productivity by 0-10 scale on the work questionnaire (people out of work scored to 0)

Ordinal logistic regression:

- Self-reported breathlessness by modified MRC Dyspnoea Scale
- Other self-reported symptoms number (count) of other symptoms experienced (grouped into 5 groups according to the distribution)

Binary logistic regression

- Whether any hours of work were missed in the past 7 days (yes/no) (people out of work set to no)
- Other self-reported symptoms binary presence/absence of each of the 22 other symptoms asked (only including in the table those with at least 10 individuals reporting that symptom at baseline). If any other self-reported symptom (from the free-text field) was reported by at least 10 people at baseline, this can also be added.

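### Coding people out of work as having missed no hours dilutes the missed-work outcome and can reverse its direction, and SAP 6.2 gives no in/out-of-work comparison at 3 months

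*SAP*

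**What the plan says.** Section 2 of the SAP sets as a secondary aim the "effectiveness for improving quality of life, reported fatigue, breathlessness, pain, sleep quality, mental health, cognitive function, work status and other symptoms at 3 months". Section 3.4.1 lists "Work status and productivity" among the secondary outcomes. Section 6.2 turns this into two items:

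- Binary logistic regression: "Whether any hours of work were missed in the past 7 days (yes/no) (people out of work set to no").
- Linear regression: "Self-reported work productivity by 0-10 scale on the work questionnaire (people out of work scored to 0").

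Section 6.2 has no model for being in or out of work at 3 months. Appendix Table 3 has rows for missed work and work productivity only. The proportion in work appears only as a baseline characteristic, in Appendix Table 1.

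On baseline adjustment, 6.2 says that "for continuous and ordinal outcomes these will be adjusted for baseline level of the same outcome", which leaves out the binary outcomes. The footnote to Appendix Table 3 describes the effects as adjusted for baseline without that limit.

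**The concern.** The value 'no' pools two opposite states: well enough to work all one's hours, and not working at all. In a condition that keeps people from work, the second state is often the worst one, yet it receives the favourable value. Movement between the states is then scored backwards, whether a participant misses hours and later stops work or comes back part-recovered.

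If the treatment changes who is in work, the odds ratio mixes that change with the change in absence among workers, and the two can pull in opposite directions. A larger sample would not cure this, because it comes from the outcome definition and not from sampling error. The result will still be printed with an effect size, confidence interval and p-value, in a trial whose stated use is to inform the design of a later one.

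**Working it through.** The SAP gives no rate, effect size or power for the work outcomes, so there is no figure to reproduce. What can be checked is the direction that the rule produces.

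**Inputs.** From the SAP: the coding rule (6.2); 1:1 allocation (3.3); and the background statement that "the trial should be halted with the initial 105 patients recruited", hence about 52 per arm. Assumed, because the SAP does not give them: the share in work and the share of workers missing hours, by arm.

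**Formulae.** Let w be the share in work and m the share of workers who missed any hours.

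- Planned outcome: P(yes) = w × m.
- In work with no hours missed: P = w × (1 − m).
- The two disagree in direction when w_A·m_A > w_P·m_P while w_A·(1 − m_A) > w_P·(1 − m_P), where A is active and P is placebo.

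**Worked counts (assumed).** Placebo: 30 in work, 12 missed hours. Active: five more in work, three of whom missed hours, so 35 in work and 15 missed.

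- Planned outcome: 15/52 = 28.8% against 12/52 = 23.1%; OR = (15/37)/(12/40) = 1.35, against the drug. 95% CI about 0.56 to 3.26.
- In work with no hours missed: (35 − 15)/52 = 20/52 = 38.5% against (30 − 12)/52 = 18/52 = 34.6%; OR = (20/32)/(18/34) = 1.18, for the drug. 95% CI about 0.53 to 2.62.

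**When the reversal vanishes.** Keep the five returners, three with absence, and let absence among the 30 existing workers on active fall below 12.

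- To 9: total 9 + 3 = 12; OR = 1.00.
- To 8: total 8 + 3 = 11; OR = (11/41)/(12/40) = 0.89, the right direction.

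**Range (assumed).** Placebo fixed at w = 50%, m = 40%, so P(yes) = 20.0% and P(out of work or missed hours) = 70.0%. An OR below 1 favours the drug.

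| Active w | Active m | P(yes), planned | OR, planned | P(out or missed) | OR, out or missed |
|---|---|---|---|---|---|
| 55% | 40% | 22.0% | 1.13 | 67.0% | 0.87 |
| 60% | 40% | 24.0% | 1.26 | 64.0% | 0.76 |
| 70% | 40% | 28.0% | 1.56 | 58.0% | 0.59 |
| 80% | 40% | 32.0% | 1.88 | 52.0% | 0.46 |
| 70% | 35% | 24.5% | 1.30 | 54.5% | 0.51 |
| 70% | 30% | 21.0% | 1.06 | 51.0% | 0.45 |

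With 70% in work on active, the planned OR returns to 1 once m falls to 0.20/0.70 = 28.6%.

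**If work status does not change.** With w = 50% in both arms and m of 30% against 40%, the planned outcome is 15% against 20%. The direction is right, but a 10-point difference among workers has become 5 points. That case is dilution, not reversal.

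**The case against.** The strongest reply is that little depends on this item. It is one of 16 named secondary outcomes in 6.2 (13 linear, two ordinal, one binary), before the individual symptoms. It is not a key secondary outcome, so section 8 does not take it further. The SAP declares the trial underpowered for its primary outcome and puts the emphasis on safety. All of that stands, and it limits the consequence. It does not make the coding right.

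The second reply is that the reversal is conditional. It needs enough net change in work status within 3 months and no sufficient fall in absence among people already working. This stands too. A reader might infer that the planned analysis will show benefit as harm; the SAP does not support that, because it gives no employment or absence rates. With the assumed counts, both confidence intervals are wide and include 1, and the complete-case rule (4.5, 6.2) would leave fewer than 52 per arm.

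The third reply is that the productivity item already covers return to work. Read plainly, 0 is the lowest productivity, so returning raises the score and stopping lowers it. A reader might therefore go too far in saying that return to work is not captured at all. A reader might also suppose that 0 means no impairment, so that both items reward being out of work; nothing in the SAP suggests this, and it runs against the item's name. What remains is that the two items place the same person at opposite ends, and that neither is the in/out-of-work comparison the objectives imply.

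**Conclusion.** The point holds as a defect in one non-key secondary outcome and should be fixed. The dilution and the scope for reversal follow from the coding rule alone. The size and actual direction depend on rates the SAP does not give: across the assumed scenarios the planned OR runs from 1.06 to 1.88 where the alternative shows benefit, and with a large enough fall in absence it drops below 1. The two work items conflict if 0 is the lowest productivity score, which is the natural reading. The missing comparison of being in work at 3 months is a plain gap between sections 2 and 3.4.1 on one side and 6.2 and Appendix Table 3 on the other. A reader might infer a threat to the trial's main conclusions; there is none, since no primary, key secondary or safety result uses this item.

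**What to change.** Make the change before unblinding; section 4.2 already bars unblinding until the SAP is approved.

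1. Replace the binary outcome with being in work and having missed no hours in the past 7 days (yes/no; out of work = no), in all participants with 3-month data, in keeping with the complete-case rule.
2. Add being in work at 3 months (yes/no) to 6.2 and Appendix Table 3.
3. State that both are adjusted for baseline work status, because the text of 6.2 provides baseline adjustment only for continuous and ordinal outcomes. Bring the Appendix Table 3 footnote into line.
4. If missed hours are also shown among workers only, label that analysis as conditional on a post-randomisation state.
5. For productivity, keep 0 for people out of work and confirm that 0 is the lowest score. Do not restrict the item to people in work at baseline, since that would drop those who return.

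The cost is SAP wording and recoding: the monthly survey in 3.4.2 already covers work status. The downside is that people out of work for reasons unrelated to health count as unfavourable, which adjustment for baseline work status only partly addresses. The recode settles the direction of the outcome. It does not by itself remove dilution: in the no-change case above it gives 35% against 30%, again 5 points.

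### Coding people out of work as having missed no hours makes leaving work count as favourable, so the missed-work result can take the wrong sign

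*SAP*

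**What the plan says.** The objectives in SAP section 2 include effectiveness for "mental health, cognitive function, work status and other symptoms at 3 months", and section 3.4.1 lists "Work status and productivity" among the secondary outcomes.

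Section 6.2 turns this into two variables:

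- a binary logistic model for "Whether any hours of work were missed in the past 7 days (yes/no) (people out of work set to no";
- a linear model for "Self-reported work productivity by 0-10 scale on the work questionnaire (people out of work scored to 0".

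For every secondary outcome, "the main analysis will be intention-to-treat complete case analysis at 3-month follow-up", so neither model is limited to people in work. On baseline adjustment, section 6.2 says that "for continuous and ordinal outcomes these will be adjusted for baseline level of the same outcome", which leaves out binary outcomes, although the footnote to Appendix Table 3 says effects are adjusted for baseline.

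Being in work is tabulated only at baseline, in Appendix Table 1. Neither section 6.2 nor Appendix Table 3 has a row for it at 3 months. Section 8 does not reach the work variables: of the secondary outcomes, it takes up the PROMIS summary score and EQ-VAS, and "only these (along with the primary outcome) will be taken forward into the additional analyses (section 8".

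**The concern.** The favourable category of the missed-hours variable mixes two opposite states: working without losing time, and not working at all. A participant who was missing hours and then stops work because of Long COVID moves from yes to no. One who was off work and returns part-time but misses an hour moves from no to yes. Both moves are scored against their meaning for an objective of improving work status.

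A treatment that keeps people in work, or brings them back, puts more people at risk of a yes. It can then be reported with an odds ratio above 1 for missed work, and a harmful treatment with one below 1. Nothing elsewhere in the SAP would reveal this: there is no 3-month count of people in work, no sensitivity analysis of the row, and no note of the coding under Appendix Table 3. Adjusting for baseline would not cure it if the baseline value carries the same coding.

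**Working it through.** The SAP gives no figure for this outcome, so there is none to reproduce. From the SAP come the coding rule, the all-participant analysis set, 1:1 allocation (section 3.3) and 105 recruited, so about 52 per arm. All work rates below are assumptions.

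**1. When the sign reverses.** Let w be the share of an arm in work at 3 months and m the share of those in work who missed hours. Under the SAP rule, P(yes) = w × m. If treatment raises w and lowers m, the coded odds ratio (treated against control) still exceeds 1 whenever wT/wC > mC/mT.

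**2. Leaving work.** Assume 60% in work at baseline, m = 0.35 in both arms, and 10% of control and 4% of treated workers leaving.

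- SAP coding: control 0.6 × 0.90 × 0.35 = 0.189; treated 0.6 × 0.96 × 0.35 = 0.2016. OR = (0.2016/0.7984)/(0.189/0.811) = **1.08**.
- Leavers counted as missed, among baseline workers: control 0.10 + 0.90 × 0.35 = 0.415; treated 0.04 + 0.96 × 0.35 = 0.376. OR = **0.85**.
- The two lines above have different denominators. With all participants kept and not in work or missed counted as unfavourable: control 1 − 0.6 × 0.90 × 0.65 = 0.649; treated 1 − 0.6 × 0.96 × 0.65 = 0.6256. OR = **0.90**. For not in work alone: 0.46 against 0.424, OR = **0.86**. The opposite direction does not come from the change of denominator.
- With 15% and 5% leaving, SAP coding gives 0.1785 against 0.1995, OR 1.15. Among baseline workers it is 0.4475 against 0.3825, OR 0.76.

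**3. Returning to work.** With the same 60% and 35%, let 5% of control and 15% of treated participants who were off work return. SAP coding: control 0.21 + 0.4 × 0.05 × 0.35 = 0.217; treated 0.21 + 0.4 × 0.15 × 0.35 = 0.231. OR = **1.08**, against the arm with more returns.

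**4. How robust the reversal is.** Take mC = 0.40 and wC from 0.4 to 0.7:

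| Gain in share in work (treated) | mT | Coded OR |
|---|---|---|
| 10 points | 0.40 | 1.21 to 1.31 |
| 10 points | 0.36 | 1.04 to 1.15 |
| 5 points | 0.36 | 0.95 to 1.01 |
| 0 to 15 points | 0.30 | below 1, except 1.04 at wC = 0.4 with a 15-point gain |
| 0 to 15 points | 0.20 | 0.42 to 0.65 |

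With no difference in w the sign holds but the effect shrinks: at w = 0.5 and mT = 0.36, the coded comparison is 0.20 against 0.18, OR 0.88, where the in-work OR is 0.84.

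**5. Precision.** For the 1.08 in step 2, the standard error of the log OR at 52 per arm is √(1/9.83 + 1/42.17 + 1/10.48 + 1/41.52) = 0.495, so the 95% interval is about 0.41 to 2.86. For the 0.85, with about 31 baseline workers per arm, it is about 0.31 to 2.35.

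**6. In counts.** Suppose 30 of 52 per arm are in work and 12 of them miss hours. If 6 of the 12 controls then leave work, the coded comparison becomes 12/52 treated against 6/52 control, OR 2.30 (interval about 0.79 to 6.69), against treatment, though only controls worsened. Merging not in work with missed hours gives 34/52 in both arms and hides the change. Separate levels show it: 22/52 treated against 28/52 control not in work.

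**The case against.** The rule keeps every complete case in the model and avoids conditioning on work status after randomisation. That is a merit, and any replacement should preserve it.

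The rates are invented, and step 2 is a favourable case for reversal because the drug affects staying in work but not hours missed. At about 31 workers per arm, 10% against 4% leaving is about three people against one. Where missed hours also fall materially, the sign mostly holds. The SAP does not define who is out of work; if someone on sick leave from a job counts as in work, the exit route narrows to actual job loss within 3 months. All of this stands, and it limits how often the rule will bite, not what the rule does.

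A reader might infer that at least one work analysis must be coded the wrong way round whatever the productivity scale's direction, so that both are suspect. This adds nothing to the missed-hours point. The natural reading of 0 on a productivity scale is no productivity; leaving work is then scored at the unfavourable end and the coding is sensible. The SAP does not state the direction, so only a confirmation is due.

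A reader might also infer that equal entry to and exit from work would remove all distortion. It would not, because step 4 shows attenuation with equal shares in work. For the sign, the net share in work is what counts.

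**Conclusion.** The coding rule is at odds with the work-status objective, and following it as written can give a wrong-signed missed-work result. Reversal needs a difference in the share in work, between arms, that outweighs the difference in missed hours; otherwise the effect is diluted or, with small differences, close to null.

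The odds ratios of 1.08 against 0.85 illustrate direction only. They rest on assumed work rates, and their intervals run well to both sides of 1. The documents do not support a claim that the sign will reverse, or that the trial would credibly report harm or benefit on work. The point concerns one non-key secondary outcome in a trial that the SAP already calls underpowered for its primary outcome. It is worth correcting because the row's direction cannot be interpreted as defined.

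**What to change.** In section 6.2, replace the binary variable with a three-level ordinal outcome in all complete cases: in work with no hours missed, in work with hours missed, not in work. Analyse it by ordinal logistic regression adjusted for the same variable at baseline, and change the Missed work row and its symbol in Appendix Table 3 to match. If the data allow, set aside people outside the labour force at baseline for reasons other than health. Define out of work, including how sick leave is treated.

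Alternatively, keep the binary row and add in work/out of work at 3 months as an outcome beside it, so that the two are read together.

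Restricting the model to people in work at baseline is not an adequate substitute: it drops everyone who could return to work and shrinks an already small sample.

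For productivity, state that 0 is the unfavourable end, and recode people out of work if it is not.

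The cost is SAP wording and a recode of work data. The row is no longer a simple yes/no, and leaving work for non-health reasons counts as worst unless the reason was recorded. If the data have already been unblinded, report the recode as an unplanned analysis, labelled as section 4.1 requires.

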8.1 Per protocol analyses

A per protocol analysis will be conducted using the per-protocol definition provided above (4.4.2) to define the treatment groups (rather than randomisation arm).

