4.4.2 Per protocol

Additional analyses on a per-protocol basis will also be conducted, in which participants will be stratified into groups in terms of whether they took the trial treatment or not. The following groups will be analysed:

- Adherers: People who took at least 50% of the intended dose of treatment for at least 60 days (2 months) out of the total 90 days of treatment.
- Non-adherers: All others.

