6.1 Primary outcome

The primary analysis of the primary outcome will be an intention-to-treat complete case analysis at 3-month follow-up, adjusted for baseline level of the same outcome. Post-Covid Functional Status Scale will be analysed using ordinal logistic regression. No other adjustments will be made for the primary analyses, although additional secondary analyses adjusting for age (above or below median) and gender will be conducted (see section 8.4 below).

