Dummy table illustrating the presentation of the primary and secondary analysis results is given in appendix table 3.

7 Evaluation of safety outcomes

A table will be presented with counts of the following adverse safety outcomes, by trial arm (appendix table 4):

- SUSAR
- Serious adverse event (SAE)
- Pregnancy
- Adverse reactions involving abnormal liver test results (adverse event designated as probably or definitely related to trial medication)
- All other adverse reactions
- Adverse events (designated possible or unlikely related to trial medication) involving abnormal liver test results
- All other adverse events (designated possible or unlikely related to trial medication)

Further description and discussion of any SUSAR, SAE, pregnancy, adverse reactions and abnormal liver test results will be provided in the text (as the numbers of these are anticipated to be few). For each abnormal liver test result, the status of liver function at baseline will be mentioned, as abnormal liver function at baseline is expected to be linked to abnormal results during follow-up (although numbers are expected to be too small to formally test this). All adverse events will be broken down into specific categories (e.g. headache, nausea, etc) by trial arm in an appendix table. We will also present adverse events by trial arm stratified by gender in the same appendix table.

Changes over time in liver function test (LFT) results by arm will be described through data visualisation. Specifically, we will plot the mean and standard error values of AST, ALT and bilirubin at baseline, month 1 and month 3 by trial arm. T-test for the differences in each LFT will be calculated at each timepoint, crudely and with adjustment for baseline level. The corresponding numerical results will be given in an appendix table.

8 Additional analyses

The following additional analyses will only be applied to primary and key secondary to avoid multiplicity of analysis results. Apart from the specific aspects mentioned, each analysis will be the same as described in section 6.

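### The per-protocol analysis in SAP 8.1 groups participants by adherence instead of randomised arm, so it is not a randomised Ashwagandha-versus-placebo comparison

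*SAP*

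**What the plan says.** Section 4.4.2 sets up the per-protocol groups: "participants will be stratified into groups in terms of whether they took the trial treatment or not". Adherers are "People who took at least 50% of the intended dose of treatment for at least 60 days (2 months) out of the total 90 days", and the other group is "Non-adherers: All others". Neither definition mentions Ashwagandha, placebo or arm.

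Section 8.1 then runs the analysis "using the per-protocol definition provided above (4.4.2) to define the treatment groups (rather than randomisation arm". The opening of section 8 adds: "Apart from the specific aspects mentioned, each analysis will be the same as described in section 6". Section 6 is a complete-case comparison adjusted for the baseline level of the outcome, and for the primary outcome section 6.1 says "No other adjustments will be made for the primary analyses".

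Section 6.2 limits the scope. It names the PROMIS-29+2 summary score and EQ-VAS as key secondary outcomes, and "only these (along with the primary outcome) will be taken forward into the additional analyses (section 8".

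**The concern.** A per-protocol analysis is normally the randomised comparison repeated in people who followed the protocol. Here the grouping variable itself is changed. Adherence is not randomised. People who keep taking tablets may differ in prognosis from those who stop, whichever tablet they were given. An adherence contrast can therefore show a benefit when the drug does nothing. On the literal reading it can also dilute a real effect, because placebo takers sit in the favoured group.

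Section 4.4.2 does not say what trial treatment means, so two analysts could build two different contrasts from the same text. The stakes are limited to a supporting analysis. However, the SAP expects the primary analysis to be underpowered and says the data will inform a future trial, so the supporting analyses should at least answer the question their label implies.

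**Working it through.** **Step 1: what enters the model.** Section 8.1 puts the adherence group in place of arm. The opening of section 8 leaves the rest of the section 6 model as it is, so arm is not a term. Appendix Table 2 records tablets taken in both arms, so placebo participants can meet the adherer definition. No section restricts the data to adherers and then compares arms. The SAP gives no figure for this analysis, so there is none to reproduce.

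**Step 2: who is compared.** From the SAP: 1:1 allocation (3.3) and 105 participants. Assumed: adherence a = 0.75 in both arms. Shares of all participants:

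- Ashwagandha adherers: 0.5 × 0.75 = 0.375
- Placebo adherers: 0.375
- Non-adherers: 0.125 in each arm, 0.25 in total

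Literal reading: 0.75 against 0.25, with half of the adherers on placebo. As-treated reading (Ashwagandha adherers against everyone else): 0.375 against 0.625, and 0.375/0.625 = 60% of the comparator are placebo adherers.

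**Step 3: continuous outcomes, no drug effect.** Assume adherers do g = 0.4 SD better for reasons unrelated to the drug. Let u, between 0 and 1, be the part of that difference that the baseline score does not capture.

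- Literal: g × u = 0.4u, so 0 to 0.40 SD.
- As-treated: g × (1 − 0.60) × u = 0.16u, so 0 to 0.16 SD.

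A simulation at N = 105 (3,000 replicates) gave 0.401 and 0.163, which match u = 1. The arm contrast within adherers gave 0.005.

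Sensitivity: both results scale with g, so g = 0.2 halves them. With equal adherence in the arms, the literal result does not depend on a. The as-treated result is g × (2 − 2a)/(2 − a) × u. At u = 1 and g = 0.4 this is 0.23 SD for a = 0.6 and 0.07 SD for a = 0.9.

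**Step 4: continuous outcomes, true effect, no confounding.** Assume a 0.4 SD effect in adherers only.

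- Literal: 0.5 × 0.4 = 0.20 SD (0.189 simulated), about half.
- As-treated: 0.40 SD, no dilution, because nobody in the comparator has a drug effect under this assumption.

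**Step 5: the ordinal primary outcome.** A proportional-odds simulation (200,000 participants) used the 3-month PCFS percentages quoted in section 3.2, 75% adherence, a drug effect in adherers only, and no baseline adjustment. An odds ratio (OR) below 1 is favourable.

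| Drug OR | Prognostic OR of adherence | Literal | As-treated | Arms within adherers |
|---|---|---|---|---|
| 1.0 | 0.5 | 0.50 | 0.77 | 1.01 |
| 0.5 | 1.0 | 0.70 | 0.50 | 0.50 |
| 0.5 | 0.5 | 0.36 | 0.39 | 0.50 |

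On the literal reading at N = 105 with no drug effect, the chance of p < 0.05 was about 5%, 10%, 37% and 73% for prognostic ORs of 1.0, 0.75, 0.5 and 0.33. These rates used a Mann-Whitney test as a proxy for ordinal regression over 4,000 runs, again without baseline adjustment.

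**The case against.** The strongest reply is that this is one of several additional analyses. The primary analysis, and the main analysis of every secondary outcome, is intention-to-treat, and the safety tables are by trial arm. That stands, and it sets the weight of the point.

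A reader might go further than the SAP allows in four ways.

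- **That placebo takers are certainly pooled with Ashwagandha takers.** This is the literal reading, but trial treatment is undefined and the as-treated reading is open. The word stratified in 4.4.2, taken alone, could even suggest arm comparisons within adherence strata. The parenthesis in 8.1 rules that out as written.
- **That the result will be presented as the effect in people who took Ashwagandha.** The SAP does not say so, and no dummy table covers this analysis.
- **That 0.40 SD is the expected bias.** It is the assumed adherer advantage handed back, with nothing removed by the baseline adjustment that section 6 specifies. It is the upper end of a range that starts near 0.
- **That the 50%-for-60-days cut-off is also an error.** Section 4.4.2 fixes it explicitly and nothing in the SAP contradicts it. Whether to set it higher is a matter of preference.

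Comparing arms among adherers is not free of bias either. It conditions on something that happens after randomisation. The near-null results for that contrast in the working hold because adherence was simulated as unrelated to arm. None of this restores a randomised comparison to 8.1 as written.

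**Conclusion.** The point holds and should be fixed. On either reading of trial treatment, the analysis labelled per-protocol drops the randomised contrast and mixes any drug effect with prognostic differences linked to adherence. That follows from the wording and needs no assumption.

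The size does rest on assumptions that the SAP does not supply. With 75% adherence in both arms, a 0.4 SD adherer advantage and no drug effect, the spurious difference is 0 to 0.40 SD (literal) or 0 to 0.16 SD (as-treated), depending on how much the baseline score absorbs. With no confounding, an effect confined to adherers is roughly halved on the literal reading only. The analyses affected are the per-protocol ones of PCFS, the PROMIS-29+2 summary score and EQ-VAS. Nothing here invalidates the intention-to-treat or safety results.

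**What to change.** Rewrite 8.1 along these lines: *The per-protocol analysis compares the randomised arms (Ashwagandha vs placebo) among participants meeting the adherer definition in 4.4.2, using the section 6 model adjusted for baseline. Because adherence is determined after randomisation, this comparison can be biased if adherence differs by arm.* Delete the parenthesis that sets randomised arm aside, and state in 4.4.2 that the adherer definition applies to the allocated tablets in either arm.

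Optionally add a complier-average effect with randomised arm as the instrument. It keeps everyone with outcome data in the analysis, but assumes that allocation affects outcome only through adherence as defined.

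The cost is SAP wording. Section 4.2 bars unblinding before the SAP is approved, so the text should be settled before then. The downsides are a smaller per-protocol set (at the assumed 75% adherence, 0.75 × 105 ≈ 79 before missing data) and the residual selection bias that the new sentence acknowledges.
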